3.5.4 Exposure to study treatment

Study medication is dispensed at randomisation and at the time points indicated in the Appendix (Section 8.1). From Day 1 to Week 14 subjects are instructed to take two tablets daily. From Week 14 to Week 52 subjects are instructed to take three tablets daily.

For the ST and ST+LT period, subjects' exposure will be presented under the first treatment received (i.e. total dapagliflozin, total saxagliptin, and placebo). Additional summaries will be presented by actual dose and treatment to account for subjects on active study medication switching to high-dose at Week 14 and subjects changing treatment or up-titrating after the third randomisation.

For the randomised withdrawal period, subjects' exposure will be presented under the treatment received after the third randomisation (i.e. accounting for subjects switching from placebo to dapagliflozin or saxagliptin).

Exposure prior to rescue medication initiation includes exposure up to and on the day of rescue medication initiation.

Treatment duration (days) will be calculated as:

- ST period: date of last dose during the ST period - date of first dose + 1,
- ST+LT period: date of last dose - date of first dose + 1,
- Randomised Withdrawal period: date of last dose - date of first dose in the Randomised Withdrawal period + 1.

Treatment duration (days) by dose (low, high) for dapagliflozin and saxagliptin will be calculated as:

For subjects who were randomised to up-titrate at Week 14:

- Low-dose: date of last dose up to Week 14 visit – date of first dose + 1,
- High-dose:
 - For the ST period: date of last dose during the ST period – date of first dose after the Week 14 visit + 1,
 - For the ST+LT period: date of last dose – date of first dose after the Week 14 visit + 1,

For subjects who were randomised to not up-titrate or were responders at Week 14 (low-dose only):

- ST period: date of last dose during the ST period - date of first dose + 1,
- ST+LT period: date of last dose - date of first dose + 1.

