- Eligible subjects who are receiving active treatment will be grouped into two separate strata for dapagliflozin and saxagliptin, and then randomised 1:1 within each strata to either discontinue background medication with metformin or to continue background medication with metformin. For subjects on active treatment who are randomised to withdraw background medication with metformin, those who are currently receiving high doses of saxagliptin (5 mg) or dapagliflozin (10 mg) will continue to receive the high doses, whereas subjects who are currently receiving low doses of saxagliptin (2.5 mg) or dapagliflozin (5 mg) will have their doses up-titrated to the high doses (saxagliptin 5 mg or dapagliflozin 10 mg). Subjects in the active treatment arms who are randomised to continue background medication with metformin will continue with their current dose of either saxagliptin or dapagliflozin.
- Eligible subjects who are receiving placebo will be randomised 1:1:1 to either withdraw background medication with metformin and switch to active treatment with either saxagliptin 5 mg or dapagliflozin 10 mg or to remain on background medication with metformin and continue with placebo.

[figure not shown]
The study design schematic for subjects not undergoing randomised withdrawal of background medication at Week 32 or Week 40 is presented in [Figure 2](#).

Figure 2 Study design schematic for subjects not undergoing randomised withdrawal of background medication at Week 32 or Week 40

The study design schematic for subjects undergoing randomised withdrawal of background medication at Week 32 or Week 40 is presented in [Figure 3](#).

[figure not shown]
Figure 3 Study design schematic for subjects undergoing randomised withdrawal of background medication at Week 32 or Week 40

*Subjects who fail to qualify at Week 26 due to HbA1c ≥ 7.5% at Week 26 may qualify at Week 32 if HbA1c < 7.5% at Week 32.

The subgroups following the third randomisation at Week 32 or Week 40 are presented in [Figure 4](#).

Figure 4 Subgroups following the third randomisation at Week 32 or Week 40

^a Subjects who fail to qualify for the third randomisation due to HbA1c ≥ 7.5% at Week 26 may qualify at Week 32 if HbA1c < 7.5% at Week 32.

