$$\text{Incidence rate} = 100 * \frac{n \text{ subjects with } \geq 1 \text{ event of interest}}{\text{sum}[\min(\text{exposure time}, \text{time to event})]}$$

The sum of min(exposure time, time to event) will be computed by summing up the minimum of exposure time or time to event per subject across all subjects for each treatment and dose as treated (defined in Section 2.1).

For analyses using first treatment as treated (total dapagliflozin, total saxagliptin, placebo), exposure time and time to event are defined as:

Exposure time (years) per subject is computed as (last date of exposure for that subject - date of first dose in the study + 1)/365.25. Time to event (years) for subjects having the event is computed as (date of onset of event – date of first dose in the study +1)/365.25.

For analyses using dose at onset of AE to account for the change in treatment and dose at the 2nd and 3rd randomisations, exposure time and time to event are defined as:

Exposure time (years) per subject for each treatment and dose as treated is computed as (last date of exposure to treatment and dose for that subject - date of first exposure to treatment and dose + 1)/365.25. Time to event (years) for subjects having the event whilst on the current treatment and dose is computed as (date of onset of event – date of first exposure to treatment and dose +1)/365.25.

For incidence rate analyses for events prior to rescue, if no event occurred prior to rescue medication initiation then the date of rescue medication initiation is used instead of last date of exposure.

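### The ST+LT treatment duration by dose in SAP 3.5.4 counts high-dose days after the third randomisation as low-dose days, and has no branch for placebo subjects switched to active drug

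*SAP*

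**What the plan says.** SAP 3.5.4 presents ST and ST+LT exposure under the first treatment received. It adds summaries by actual dose and treatment, meant to account for the Week 14 dose change and for "subjects changing treatment or up-titrating after the third randomisation". The formulas follow the line "Treatment duration (days) by dose (low, high) for dapagliflozin and saxagliptin will be calculated as", and there are two branches:

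- "For subjects who were randomised to up-titrate at Week 14": low-dose time ends at the Week 14 visit. High-dose time runs from the first dose after that visit to the last dose of the period.
- "For subjects who were randomised to not up-titrate or were responders at Week 14 (low-dose only": one low-dose interval and no high-dose interval. For the long period it is "ST+LT period: date of last dose - date of first dose + 1".

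SAP 1.2 changes doses again at Week 32 or Week 40. Active-arm subjects on the low dose who are randomised to stop metformin "will have their doses up-titrated to the high doses (saxagliptin 5 mg or dapagliflozin 10 mg". Active-arm subjects who continue metformin keep their current dose. Eligible placebo subjects are allocated 1:1:1, and two of the three allocations "withdraw background medication with metformin and switch to active treatment with either saxagliptin 5 mg or dapagliflozin 10 mg".

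Three other places in the SAP do follow the actual dose:

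- Section 3.4.1, for incidence rates by dose at onset, defines exposure time from "last date of exposure to treatment and dose for that subject - date of first exposure to treatment and dose + 1", expressed in years.
- Section 4.1.6 assigns subjects to the dose received and treats Week 32/40 as a planned dose change.
- Appendix 8.13 lists exposure, with AEs and laboratory data, under the actual-dose grouping. Its drug totals there take in all three randomisations.

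**The concern.** The second branch calls its subjects low-dose only because of what happened at Week 14, but the design moves some of them to the high dose later. Applied as printed, the formula credits those later days to the low dose and gives these subjects no high-dose time. A subject first randomised to placebo fits neither branch, so later high-dose days do not enter the by-dose calculation at all. The section therefore does not deliver what it promises about the third randomisation.

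What is at stake is the ST+LT exposure table by dose. It would overstate low-dose and understate high-dose exposure in a paediatric safety database. It would also disagree with the AE and laboratory rate tables, which carry the same dose columns but measure time by the section 3.4.1 definition.

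**Working it through.** The plan states no figure for this quantity, so there is none to reproduce. The check applies the printed formula to on-schedule subjects and compares it with the dose assigned under SAP 1.2.

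**Inputs**

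- Target days, SAP Table 10: Week 32 = Day 225, Week 40 = Day 281, Week 52 = Day 365.
- First dose on Day 1 and last dose on Day 365 (assumption: on schedule, no early discontinuation).
- RWSTDT, the date of the first dose in the randomised withdrawal period (defined under SAP Table 10), falls on the visit day or the day after. Both are shown.

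**Formulas**

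- Printed low-dose duration, second branch: 365 − 1 + 1 = 365 days. Printed high-dose duration: 0.
- Assigned low-dose days: (RWSTDT − 1) − 1 + 1 = RWSTDT − 1.
- Assigned high-dose days: 365 − RWSTDT + 1.
- Overstatement of low-dose time: 365 / (RWSTDT − 1) − 1.

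**Low-dose subject randomised to withdraw metformin**

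| Switch visit | RWSTDT (day) | Printed low / high | Assigned low / high | Low-dose overstatement | Share of the 365 days misassigned |
|---|---|---|---|---|---|
| Week 32 | 225 | 365 / 0 | 224 / 141 | 365/224 − 1 = 62.9% | 141/365 = 38.6% |
| Week 32 | 226 | 365 / 0 | 225 / 140 | 365/225 − 1 = 62.2% | 140/365 = 38.4% |
| Week 40 | 281 | 365 / 0 | 280 / 85 | 365/280 − 1 = 30.4% | 85/365 = 23.3% |
| Week 40 | 282 | 365 / 0 | 281 / 84 | 365/281 − 1 = 29.9% | 84/365 = 23.0% |

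**Placebo switcher.** High-dose days are 140–141 (Week 32) or 84–85 (Week 40). The by-dose formulas give no value. The separate randomised-withdrawal duration in the same section, last dose minus first dose in that period + 1, gives exactly these days.

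**Subjects who are handled correctly.** Those up-titrated at Week 14 are already on the high dose and stay on it whether or not they stop metformin. Low-dose subjects who continue metformin stay on the low dose. ST durations end at Week 26, before the third randomisation.

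**Group level.** If n32 and n40 low-dose subjects withdraw metformin at Weeks 32 and 40, the table moves about 140·n32 + 84·n40 days from high dose to low dose. The documents give neither count, so no group-level percentage can be stated.

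**Comparison with section 3.4.1.** For the Week 32 subject, that definition gives 224–225 low-dose and 140–141 high-dose days. The two sections thus yield different person-time for the same subject and dose.

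**The case against.** The strongest reply is that the SAP already contains the right rule. Section 4.1.6 and Appendix 8.13 group actual-dose outputs, exposure included, by the dose received. The amendment history shows that the actual-dose exposure summaries were added in V3.1, so the Week 14 branches may be older text that was not updated, although the SAP does not say so. A programmer guided by those sections would split at the switch. This shows that the intention was sound, but it does not repair the formula. Section 3.5.4 gives an explicit calculation, and the grouping rules conflict with it rather than replace it.

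Three limits stand, and each rules out a stronger reading:

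- A reader might infer that safety rates by dose use wrong denominators. The documents do not support that, because dose-at-onset incidence rates take their exposure time from section 3.4.1, which handles the second and third randomisations.
- A reader might infer that placebo switchers' active-drug time is lost. It is not. The randomised-withdrawal duration counts it under the treatment received after the third randomisation, and section 4.3.1 summarises it. What is missing is a branch in the by-dose ST+LT calculation.
- A reader might take 62% or 30% as the distortion of the whole table. These are per-subject figures. They apply only to subjects on metformin alone, with HbA1c below 7.5% at Week 26 or 32, not rescued, still on study drug, on the low dose, and allocated (1:1) to withdraw metformin.

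**Conclusion.** The point holds in a bounded form. As printed, the ST+LT by-dose duration is wrong for low-dose subjects randomised to withdraw metformin: about 140 high-dose days (Week 32) or 84 (Week 40) are counted as low dose. It is also incomplete for placebo switchers. Both faults contradict the section's stated purpose and the actual-dose grouping elsewhere in the SAP.

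The day counts assume on-schedule visits and dosing to Day 365. Delayed visits or early discontinuation would change the numbers but not the direction. This is an inconsistency between definitions. It does not touch the ST exposure summary, the dose-at-onset incidence rates, or any efficacy analysis or test. It is worth correcting because the rule is wrong as written, the affected table would not reconcile with its companion safety tables, and the correction is cheap.

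**What to change.** In SAP 3.5.4, for the ST+LT period:

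1. For subjects randomised to withdraw metformin while on the low dose, end low-dose time at the last dose before RWSTDT. Count high-dose time from RWSTDT to the last dose.
2. Add a branch for placebo subjects switched to active drug, giving high-dose time of the assigned drug from RWSTDT to the last dose.
3. State that active-arm subjects who continue metformin stay under their current dose. Going through the third randomisation must not by itself start a high-dose interval.

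Alternatively, replace the by-dose bullets with the section 3.4.1 definition: last minus first date of exposure to each treatment and dose, plus 1, in days. This gives the same result and leaves one definition for all actual-dose outputs.

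The cost is one SAP definition and a small programming change. RWSTDT is already defined, and no new data are needed.

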3.5.5 Exposure to rescue medication

If a subject has rescue insulin records with overlapping start and end dates, then maximum total daily dose of rescue insulin will be calculated as:

- If the rescue insulin records have different preferred names then the total daily dose for each record will be summed,
- If the rescue insulin records have the same preferred name then from the start of overlap the maximum total daily dose will be the total daily dose from the rescue insulin record with the larger dose.

Partial rescue insulin start and end dates are imputed as defined in Appendix 8.4.

3.5.6 Treatment compliance

Treatment compliance (%) for the study medication during the treatment period is defined for each subject as $100 \times$ the number of tablets taken over the period divided by the number of tablets that should have been taken in that treatment period (the sum of the number of the tablets that should have been taken in each exposure record within that period). Compliance will be derived based only on complete dispensed and returned information (i.e. no imputation will be done on fully missing returned kits, missing returned date, or unknown number of returned tablets) and corresponding exposure records. If one or more kits (including unscheduled kits) for a visit were not returned, then the kits and exposure record for that visit are not used in the compliance calculation.

Compliance for the ST period will sum visits from Day 0 up to and including Week 26, compliance for the ST+LT period will sum all visits, and compliance for the randomised withdrawal period will sum visits after the third randomisation (Week 32 or Week 40 as applicable).

- The number of tablets taken in a period is: n dispensed (70 tablets \times the number of kits dispensed) - n returned during that period.
- The number of tablets that should have been taken for each exposure record is calculated as follows:

For exposure records up to and including Week 14 visit (or early treatment discontinuation for subjects who discontinue treatment prior to Week 14):

- (Date of last dose in the visit – date of first dose in the visit +1) X 2 tablets/day

For exposure records after Week 14 visit:

- (Date of last dose in the visit – date of first dose in the visit +1) X 3 tablets/day

If the subject underwent the third randomisation to withdrawal from metformin, then the number of tablets that should have been taken in the randomised withdrawal period is:

- (Date of last dose - date of first dose + 1) X 3 tablets/day, for visits after the third randomisation (Week 32 or Week 40 as applicable)

A subject is considered compliant if overall treatment compliance is between $\geq 80\%$ and $\leq 120\%$ of that prescribed. If compliance cannot be calculated for a subject, then their compliance will be presented as Unknown in the summary tables.

3.6 Pharmacokinetic/ pharmacodynamic assessments

Blood samples for determination of plasma levels of dapagliflozin, saxagliptin and its metabolite 5-OH-saxagliptin will be taken at the times presented in the Appendix Section 8.1 (Table 17). In addition, FPG will be collected at pre-dose and 2 hours post dose, and DPP-4 activity will be taken at the times presented in the Appendix Section 8.1 (Table 17) for the pharmacodynamic assessments. Plasma concentration data will be summarised as part of this SAP and included in the CSR.

Pharmacokinetics and exposure-response relationship analysis will be summarised and reported in a separate report as needed. If such a report is produced, full details of the analytical methods used will be described.

4. ANALYSIS METHODS

4.1 General principles

SAS version 9.4, or higher, will be used to produce all tables, listings, and figures. All table, listing, and figure specifications are provided as separate documents; these must be read in conjunction with the corresponding SAP version.

The confirmatory analyses of the primary and secondary endpoints within each drug (dapagliflozin vs. placebo and saxagliptin vs. placebo) will be performed using a hierarchical testing approach within each drug at the two-sided 0.05 level (with corresponding 95% CIs). No comparisons will be performed between dapagliflozin and saxagliptin.

When fitting models which involve the stratification variables, in case of non-convergence the stratification level may be combined with other levels or one or more stratification variables may be removed from the model.

For each imputation and statistical model described below adjusted on randomisation strata, in case of non-convergence (i.e.: because of sparse data), the following back-up models will be used in the presented order:

- 1) Remove randomisation strata of sex,
- 2) Remove randomisation strata of sex and age,
- 3) Remove randomisation strata of sex and age and collapse randomisation strata of background medication in two modalities to present (metformin only and insulin only grouped with metformin + insulin),
- 4) Remove randomisation strata of sex, age and background medication.

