performed as determined by the Investigators during the 6-month screening period. Retesting/reassessment frequencies are at the discretion of the Investigators, but should occur at least once every 3 months. In cases when a subject does not meet one or more criteria the first time and is later reassessed to see if he/she will meet that criteria, the Investigator should ensure that other criteria are still met (and have not become disqualifying during the interim time period) before accepting that the subject meets all eligibility criteria. Subjects who fail to meet the eligibility criteria after the 6-month screening period should be considered as screen failures and withdrawn from the study. Screen-failed subjects, however, can be re-screened a maximum of two more times at a later time. For re-screening, subjects must be re-consented and all the screening procedures must be repeated. Subjects are not able to be re-screened if they turn 18 years of age during the screening period.

Prior to randomization on Day 1, subjects will be required to have been treated with diet and exercise and stable dose of at least 1000 mg metformin (IR or XR) for a minimum of 8 weeks, or a stable baseline dose of insulin for a minimum of 8 weeks, or a stable combination of at least 1000 mg metformin (IR or XR) and insulin for a minimum of 8 weeks. At least 50% of subjects will be on a stable baseline dose of metformin, with or without concurrent insulin therapy. At least 30% of total subjects will be between the ages of 10 and 14 years and at least one third, but no more than two thirds, female subjects.

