4.1.10 Proportion of subjects with a pre-defined characteristic (responders) at Week t

The proportion of subjects with a *pre-defined characteristic (responders)* at Week t will be analysed using a weighted or unweighted logistic regression when there are at least 5 responders by treatment group. For proportion of responders (e.g., meeting HbA1c criteria), estimates, confidence intervals, and tests will be obtained using a weighted or unweighted logistic regression. Odds ratios (and corresponding standard errors [SE]) representing the responder odds in the dapagliflozin/saxagliptin treatment group (or regimen) versus placebo group will be generated adjusted for baseline variable (e.g., adjustment for baseline HbA1c) and each randomisation stratification factor using the SAS LOGISTIC procedure.

The frequencies of response/non-response and the associated crude response rates (as percentages) will be presented by treatment group (or regimen). In addition, weighted or non-weighted adjusted percentages, standard errors, and 95% CIs for each treatment group (or regimen) will also be displayed. Adjusted odd ratio and corresponding 95% Log likelihood confidence interval, and p-values (uncorrected) will also be presented.

For the HbA1c responder endpoints, if there is no missing data for all treatment groups in the analysis at Week t, then the logistic regression model or Fisher's exact test will be run on the non-imputed data and no combining of results from each imputed data set is necessary.

In case of non-convergence because of sparse data subsequent backup models will be used in removing randomisation strata in sequential order and/or collapsing the randomisation strata of background medication as defined in Section 4.1. A subsequent back-up model in the order presented Section 4.1 will only be provided if the preceding back-up model does not converge.

When there are less than 5 responders in any treatment group, the unadjusted (and difference) proportions, weighted or non-weighted exact 95% confidence interval, and p-values from the weighted or unweighted Fisher's exact test (when applicable) will be provided.

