4.4.3 Subgroup analyses for primary endpoint

4.4.3.1 Analysis of change from baseline in HbA1c at Week 26 within subgroups

The subgroup-by-treatment interaction will be assessed for the primary efficacy endpoint using the MI-WO imputation method and the ANCOVA model used for the primary analysis of the change from baseline in HbA1c at Week 26 with subgroup, and subgroup-by-treatment interaction as additional effects. Separate imputation models for each subgroup will be used. This will be repeated for subgroups based on race, ethnicity, sex, age group (using randomisation strata), region, baseline antidiabetic treatment, baseline HbA1c, and baseline BMI, using the categories defined in the Appendix (Table 19). The adjusted mean changes from baseline, SEs, 95% CIs, and p-value for each subgroup and the nominal p-value for subgroup by treatment interaction will be calculated.

The subgroup by treatment interaction p-value will be calculated as the median p-value from the set of all imputations.

Models for subgroup analyses which evaluate baseline HbA1c level will include terms for the categorised baseline HbA1c level and not (continuous) baseline values.

Statistical significance of a Week 26 treatment regimen*subgroup interaction will be assessed at an unadjusted 0.10 level.

In addition, a forest plot of adjusted mean difference from placebo \pm 95% confidence interval (CI), p-values for each subgroup category and p-value for interaction by subgroup will be displayed.

Subjects with missing data for the grouping variable will be excluded from the corresponding subgroup analysis. For each subgroup, if, in any treatment group, the number of subjects is less than 10 for a subgroup category, adjusted estimates and their differences and corresponding

statistics will not be displayed for that subgroup, and only descriptive statistics will be presented for that category and included in the analysis results. Interaction p-value will not be provided either.

For baseline antidiabetic treatment subgroup, if the number of subjects within ‘insulin only’ or ‘metformin + insulin’ category is less than 10, then these two categories will be grouped into ‘insulin +/- metformin’. In case of non-convergence because of sparse data, subsequent backup imputation models will be used collapsing the randomisation strata of background medication as defined in Section 4.1 and collapsing the region into ‘North America + Europe’ and ‘Rest of the World’.

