Change from baseline HbA1c at all scheduled time points up to and including Week 26 will be compared between the subjects who are Up-titration Randomised to remain on the low-dose and the subjects who are up-titration randomised to the high-dose using the ANCOVA model described in Section 4.1.9, without weights. The analysis will be evaluated in each imputed data set and the results will be combined using Rubin's rules as described in Section 4.1.12.4. The indicator for background medication used in the multiple imputation step for insulin only and insulin with metformin will be grouped as defined in Section 4.1.12. No weights will be used in the multiple imputation or ANCOVA for this analysis.

4.5.10.1 Sensitivity analysis for secondary endpoint of mean reduction in HbA1c from baseline at Week 26 between the high-dose and the low-dose in subjects who do not achieve an HbA1c < 7% at Week 12 excluding data following rescue medication initiation/early treatment discontinuation

The above analysis (Section 4.5.10) for the comparison of mean reduction in HbA1c from baseline at Week 26 between the high-dose and the low-dose in subjects who do not achieve an HbA1c < 7% at Week 12 will be repeated excluding data following rescue medication initiation or early treatment discontinuation but missing data will be imputed assuming MAR as described in Section 4.1.12.5. No weights will be used in the multiple imputation or ANCOVA for this analysis.

4.5.10.2 Metformin subgroup analysis for comparison of mean reduction in HbA1c from baseline at Week 26 between the high-dose and the low-dose in subjects who do not achieve an HbA1c < 7% at Week 12

The ANCOVA model used for the primary analysis (Section 4.5.10) of the mean reduction in HbA1c from baseline at Week 26 between the high-dose and the low-dose in subjects who do not achieve an HbA1c < 7% at Week 12 will also be repeated for the subgroup of subjects on a stable baseline dose of metformin IR or XR (with or without insulin). The same multiple imputation method used for the primary analysis of the endpoint will be used for this subgroup analysis. The indicator for background medication used in the multiple imputation step for insulin only and insulin with metformin will be grouped as defined in Section 4.1.12. No weights will be used in the multiple imputation or ANCOVA for this analysis.

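### The back-up ladder in SAP 4.1 has no step that pools the two insulin strata while keeping sex and age, so a sparse insulin-only level can cost two randomisation factors unnecessarily

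*SAP*

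**What the plan says.** SAP 4.1 states that "in case of non-convergence (i.e.: because of sparse data), the following back-up models will be used in the presented order". The list opens with "Remove randomisation strata of sex". The second step removes sex and age. The third is to "Remove randomisation strata of sex and age and collapse randomisation strata of background medication in two modalities to present", with metformin only as one level and the two insulin groups as the other. The fourth removes all three factors. SAP 4.1.10 repeats for the responder models that "subsequent backup models will be used in removing randomisation strata in sequential order", adds that background medication may be collapsed as defined in 4.1, and allows each back-up only if the one before it fails.

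A looser sentence above the list says that "the stratification level may be combined with other levels or one or more stratification variables may be removed from the model". The list then fixes the order.

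Simplifications are carried forward. SAP 4.1.12.2 and 4.1.12.3 simplify the imputation model and the ANCOVA together, and SAP 4.4.1 requires the primary ANCOVA to follow any collapsing in the imputation model.

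On stratum sizes, Protocol 3.1 sets floors for sex (one third to two thirds female) and age (at least 30% aged 10 to 14). For background medication it says only: "At least 50% of subjects will be on a stable baseline dose of metformin, with or without concurrent insulin therapy". That caps insulin only at 50% and sets no minimum.

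SAP 4.4.3.1 has a rule beginning "For baseline antidiabetic treatment subgroup, if the number of subjects within": if the insulin-only or the metformin-plus-insulin category has fewer than 10 subjects, the two are grouped. For sparse data in the same subgroup models it collapses background medication and region.

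**The concern.** Sex and age are two-level factors protected by recruitment floors. Background medication has three levels, and nothing protects the smallest. If an imputation model contains no insulin-only child, or if no insulin-only child responds in a logistic model, that level's coefficient cannot be estimated. Removing sex and age does not change this. The ladder then arrives at the pooling that would usually have sufficed, with the other two randomisation factors already discarded.

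At stake is pre-specified adjustment in the primary ANCOVA, through the carry-over rule, and in responder tests 6 to 8 of the confirmatory chain. Dropping covariates does not bias a randomised comparison, so this is a question of precision and of keeping to the planned adjustment.

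**Working it through.** **1. The plan's own figure.** Inputs from Protocol 8.1 and SAP 1.3: difference 0.75, SD 1.7, two-sided alpha 0.05, about 81 per arm.

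Power = Φ(0.75 / (1.7 × √(2/81)) − 1.96) = Φ(2.808 − 1.960) = 80.2%. The stated figure of about 80% reproduces.

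**2. Coefficients per imputation model** (SAP 4.1.12 and 4.1.12.2).
- Full model: intercept, sex, age, two background indicators, baseline = 6.
- Current ladder: step 1 has 5, step 2 has 4, step 3 has 3, step 4 has 2.
- Pooling first with sex and age kept: 5.
- Retrieved drop-out imputation (MI-RD) is allowed with as few as 5 observations per model.

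**3. Chance that a model contains no insulin-only child**, (1 − p)^n, for assumed shares p of 5%, 10% and 20%:
- n = 5: 77%, 59%, 33%
- n = 10: 60%, 35%, 11%
- n = 15: 46%, 21%, 4%
- n = 81: 1.6%, 0.02%, about 0

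The exposure is therefore in the retrieved drop-out models. A model fitted to a whole arm, such as the wash-out model fitted to placebo, rarely has an empty level.

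**4. Which step resolves the failure.** The design matrix was simulated 4,000 times per setting. Assumed: 50% metformin only, 50% male, 45% aged 10 to 14. Failure means a rank-deficient matrix or no residual degrees of freedom, as a stand-in for non-convergence, which the SAP does not define. The last three columns are shares of failed full models.

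| Retrieved drop-outs | Insulin only | Full model fails | Steps 1–2 resolve | Pool first, keep sex and age | Current step 3 resolves |
|---|---|---|---|---|---|
| 5 | 5% / 10% / 20% | 100% in all | 19% / 34% / 50% | 0% in all | 94% / 93% / 94% |
| 6 | 5% / 10% / 20% | 100% in all | 25% / 43% / 63% | 80% / 80% / 81% | 97% in all |
| 8 | 5% / 10% / 20% | 70% / 49% / 29% | 4% / 10% / 24% | 93% / 89% / 81% | 99% / 99% / 97% |
| 10 | 5% / 10% / 20% | 60% / 38% / 16% | 1% / 3% / 13% | 99% / 97% / 91% | 100% / 100% / 99% |
| 15 | 5% / 10% / 20% | 47% / 21% / 4% | 0% / 0.2% / 2% | 100% / 99.8% / 98% | 100% in all |

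A repeat run agreed to within about two percentage points. At 5 drop-outs the problem is the number of terms, and pooling alone cannot work. A second rung that also removes sex (4 coefficients) then succeeds in about 82% of cases and still keeps age.

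**5. Responder models.** The chance of no responder among n insulin-only children is (1 − r)^n, with n and the response rate r assumed:
- n = 5: 33% at r = 20%, 59% at r = 10%
- n = 7: 21% and 48%
- n = 10: 11% and 35%

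SAP 4.1.10 sends a comparison to Fisher's exact test, without adjustment, when any group has fewer than 5 responders. The chance that at least one of two groups falls below 5 is 1 − [1 − P(X ≤ 4)]². With 69 per arm and 10% response this is 31%. For test 11, with an assumed 20 per group, it is 86% at 20% response and over 99% at 10%.

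**6. Cost of losing sex and age in the primary analysis.** Replace SD 1.7 by 1.7 × √(1 − R²), where R² is the assumed share of variance explained by sex and age.
- R² = 0: 80.2%
- R² = 1%: 80.6%
- R² = 5%: 82.1%

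The loss is about 0.4 to 2 percentage points, and only in a trial where the ladder is triggered.

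**The case against.** A reader might infer that insulin only is the likely cause of any failure. The documents do not show this. They give no count for the stratum, and the rule in SAP 4.4.3.1 is a contingency that names metformin plus insulin equally. Nor does SAP 4.5.10 settle it by saying that the background indicator "for insulin only and insulin with metformin will be grouped as defined in Section 4.1.12". The same sentence recurs in metformin subgroup analyses such as 4.4.3.2, where insulin-only children are excluded by definition, and it is missing from the parallel main FPG analysis in 4.5.11.

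A reader might also infer that the ladder never cures the problem. It does: step 3 makes the needed collapse. The defect is what has been discarded by then.

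Other points against also have force:
- At the minimum of 5 retrieved drop-outs, shedding terms is what helps, and pooling alone fails.
- The SAP does not say that one non-converging imputed data set triggers the ladder. With no responders in one level, only that level's coefficient diverges; in a simulation with assumed inputs the treatment log-odds ratio stayed finite and differed from the pooled model by 0.05 to 0.07 on average.
- Test 11 will mostly go to Fisher's exact test, and the rescue models are exploratory under SAP 4.6, so neither adds much.
- The current order keeps the three-level regimen factor longest, which is a defensible preference, and a fixed order leaves no data-driven choice.

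These points limit the size of the problem. They do not supply the missing step. The permissive sentence in SAP 4.1 does not supply it either, because the ladder that follows must be taken in the listed order.

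**Conclusion.** The gap is real and minor. If insulin only is the sparse level, steps 1 and 2 resolve between 0% and 24% of failures with 8 to 15 retrieved drop-outs, against 81% to 100% for pooling first with sex and age kept (assumed insulin-only share 5% to 20%). The primary ANCOVA can then lose two of its three randomisation factors, and responder tests 6 to 8 can lose them as well. The price is a small avoidable loss of precision: 80.2% power against 80.6% to 82.1%, for an assumed 1% to 5% of variance explained. Validity and type I error are not in question.

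The result rests on assumed stratum shares and drop-out numbers, and on rank deficiency as the meaning of non-convergence. For the primary analysis it matters mainly if retrieved drop-out imputation is used.

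**What to change.** Reorder the ladder in SAP 4.1:
1. Collapse background medication to metformin only versus insulin with or without metformin, keeping sex and age.
2. Also remove sex.
3. Also remove age.
4. Remove background medication.

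State that when an imputation model has too few observations for step 1, for example 5 retrieved drop-outs, the analysis goes on to step 2.

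The last two models are the same as in the current ladder, so the new one converges wherever those do. The pooled indicator is already defined in SAP 4.1.12. The cost is four lines of text, with no new data and no effect when the full model converges. The one thing given up is the three-level background factor in those failures that dropping sex or age alone would have resolved.

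Also reconcile the stratification itself. Protocol 4.4 describes two background levels (metformin alone, insulin with or without metformin), whereas the Protocol synopsis, Protocol 3.1 and 8.1, and SAP 1.2 and 1.3 describe three. If the randomisation system used two, the pooled factor is the actual stratification factor and the case for pooling first is stronger.
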